8.1.3.2. Sleep-Loss

Participants will assess their Sleep-Loss due to pruritus. They will rate their sleep based on a 5-point Likert scale: 0 (not at all) to 4 (unable to sleep at all).

Participants will record their Sleep-Loss assessments daily using an electronic diary at home. As indicated in the SoA (Section 1.3), initial electronic diary entries for Sleep-Loss should be completed a minimum of 4 of 7 days before randomization.

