8.1.3.3. Skin Pain Numeric Rating Scale (NRS)

Skin Pain NRS (Newton et al. 2019) is a patient-administered, validated, 11-point horizontal scale anchored at 0 and 10, with 0 representing “no pain” and 10 representing “worst pain imaginable.” Overall severity of a patient’s skin pain is indicated by selecting the number that best describes the worst level of skin pain in the past 24 hours.

Participants will record the Skin Pain NRS assessments daily using an electronic diary at home. As indicated in the SoA (Section 1.3), initial electronic diary entries for Skin Pain NRS should be completed a minimum of 4 of 7 days before randomization.

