6.4. Handling of Dropouts or Missing Data

Depending on the estimand being addressed, different methods will be used to handle missing data. The description of estimands can be found in Section [6.2](#).

[Table KGAK.6.4](#) describes the planned imputation methods for efficacy and health outcome endpoints for the treatment period.

Table KGAK.6.4. Imputation Techniques for Various Variables During Treatment Period

Type of Endpoints	Efficacy and Health Outcome Endpoints	Estimand of Secondary Endpoints (Analysis Strategy for Intercurrent Events)	Missing Data Imputation Method (Analysis Method)
Categorical	IGA, EASI, Pruritus NRS, Skin Pain NRS, and Sleep-loss related categorical endpoints at prespecified timepoints	Primary Estimand (Hybrid)	MCMC-MI (CMH)
		Supportive Estimand (Composite)	NRI (CMH)
	Remaining categorical endpoints	Supportive Estimand (Composite)	NRI (CMH)
Continuous	EASI percent change, Pruritus NRS percent change, Skin Pain NRS percent change, and Sleep-loss change from baseline	Primary Estimand (Hybrid)	MCMC-MI (ANCOVA)
		Supportive Estimand (Hypothetical)	No imputation (MMRM)
	Remaining continuous endpoints collected at multiple postbaseline timepoints including (but not limited to) BSA and POEM	Supportive Estimand (Hypothetical)	No imputation (MMRM)
	Remaining continuous endpoints collected only once postbaseline (if any)	Supportive Estimand (Hypothetical)	LOCF (ANCOVA)

Abbreviations: ANCOVA = analysis of covariance; BSA = body surface area; CMH = Cochran-Mantel-Haenszel; EASI = Eczema Area and Severity Index; IGA = Investigator's Global Assessment; LOCF = last observation carried forward; MCMC-MI = Markov chain Monte Carlo multiple imputation; MMRM = mixed-model repeated measures; NRI = nonresponder imputation; NRS = Numeric Rating Scale; POEM = Patient-Oriented Eczema Measure.

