The approach of handling missing data for Pruritus NRS, Skin Pain NRS, and Sleep-loss are the same. Using Pruritus NRS as an example, for derivation of the following Pruritus NRS responses, no rounding will be performed. The imputed Pruritus NRS value will be compared directly to the observed mean baseline Pruritus-NRS value to determine whether a response was achieved:

- Percentage of participants with a Pruritus NRS of ≥ 4 -points at baseline who achieve a ≥ 4 -point reduction from baseline at Week 16

Imputation of continuous data will parallel that of binary variables. The imputed values will be used for the secondary endpoints, such as

- Percentage change in Pruritus NRS from baseline
- Percentage change in EASI score from baseline
- Percentage change in Skin Pain NRS from baseline.

Table KGAK.6.5. Seed Values for MCMC-MI

Analysis	Seed values	
	Lebrikizumab 250 mg Q2W	Placebo
IGA and its related derived endpoints	970309630	1477266806
EASI and its related derived endpoints	353985587	1828572477
Pruritus NRS and its related derived endpoints	1611917356	1087836192
Skin Pain NRS and its related derived endpoints	345235233	352342343
Sleep-loss score and its related derived endpoints	574563534	645745224

Abbreviations: EASI = Eczema Area and Severity Index score; IGA = Investigator's Global Assessment; MCMC-MI = Markov chain Monte Carlo multiple imputation; NRS = Numeric Rating Scale; Q2W = every 2 weeks.

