Sleep-loss due to pruritus	
Sleep-loss due to pruritus will be assessed by the participant.
 
Participants rate their sleep based on a 5-point Likert scale (0 [not at all] to 4 [unable to sleep at all]).
 
Assessments will be recorded daily by the participant using an electronic diary.
	Sleep-loss prorated weekly mean score	
The prorated weekly mean is based on previous 7 days. If the participant has at least 1 daily score, the weekly mean is the prorated average of daily scores within the given week. Single item; range 0 to 10.
 
eDiary data are mapped to study visit per Appendix 1.
	Weekly mean score missing if the participant has no Sleep-loss due to pruritus responses within the week.
		Change from baseline in Sleep-loss prorated weekly mean score	Change from baseline: observed sleep loss prorated weekly mean score – baseline sleep loss score	Missing if baseline or observed value is missing.
		Percent change from baseline in Sleep-loss prorated weekly mean score	Percentage change from baseline: $100 \times \frac{\text{Observed score} - \text{Baseline}}{\text{Baseline}}$	
Skin Pain NRS	
Skin Pain NRS is a participant-administered, validated, 11-point horizontal scale anchored at 0 and 10, with 0 representing “no pain” and 10 representing “worst pain imaginable.” Overall severity of a participant’s skin pain is indicated by selecting the number that best describes the worst level of skin pain in the past 24 hours.
 
Assessments will be recorded daily by the participant using an electronic diary.
	Skin Pain NRS prorated weekly mean score	
The prorated weekly mean is based on previous 7 days. If the participant has at least 1 daily score, the weekly mean is the prorated average of daily scores within the given week. Single item; range 0 to 10.
 
eDiary data are mapped to study visit per Appendix 1
	Weekly mean score missing if the participant has no Skin pain NRS responses within the week.
		Change from baseline in Skin Pain NRS prorated weekly mean score	Change from baseline: observed Skin Pain prorated weekly mean score – baseline Skin Pain weekly mean score	Missing if baseline or observed value is missing.
		Percent change from baseline in Skin Pain	Percentage change from baseline: $100 \times \frac{\text{Observed score} - \text{Baseline}}{\text{Baseline}}$	

		NRS prorated weekly mean score		

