Sleep-loss Score	Percent Change from baseline in Sleep-loss Score	ANCOVA with MCMC-MI	mITT	LEB 250 mg Q2W vs PBO; Week 16 and all scheduled visits in the Treatment Period	Secondary analysis
	Change from baseline in Sleep-loss Score	MMRM	mITT	LEB 250 mg Q2W vs PBO; Week 16 and all scheduled visits in the Treatment Period	Supplementary analysis
		CMH analysis with MCMC-MI	mITT participants with baseline Sleep-loss ≥ 2	LEB 250 mg Q2W vs PBO; Week 16 and all scheduled visits in the Treatment Period	Secondary analysis

Measure	Variable	Analysis Method (Section 6.1)	Population (Section 6.1.1)	Comparison/Time Point	Analysis Type
	Proportion of participants achieving at least 2-point improvement in sleep-loss in participants who had baseline Sleep-loss ≥ 2	CMH analysis with NRI	mITT participants with baseline Sleep-loss ≥ 2	LEB 250 mg Q2W vs PBO; Week 16 and all scheduled visits in the Treatment Period	Supplementary analysis
Skin Pain NRS	Percent Change from baseline in Skin Pain Score	ANCOVA with MCMC-MI	mITT	LEB 250 mg Q2W vs PBO; Week 16 and all scheduled visits in the Treatment Period	Secondary analysis
	Change from baseline in Skin Pain Score	MMRM	mITT	LEB 250 mg Q2W vs PBO; Week 16 and all scheduled visits in the Treatment Period	Supplementary analysis
	Proportion of participants achieving at least 4-point improvement in Skin Pain NRS in participants who had baseline Skin Pain NRS ≥ 4	CMH analysis with MCMC-MI	mITT participants with baseline Skin Pain NRS ≥ 4	LEB 250 mg Q2W vs PBO; Week 16 and all scheduled visits in the Treatment Period	Secondary analysis
		CMH analysis with NRI	mITT participants with baseline Skin Pain NRS ≥ 4	LEB 250 mg Q2W vs PBO; Week 16 and all scheduled visits in the Treatment Period	Supplementary analysis
Patient-Oriented Eczema Measure (POEM)	Change from baseline in POEM score	MMRM	mITT	LEB 250 mg Q2W vs PBO; Week 16 and all scheduled visits in the Treatment Period	Secondary analysis
Patient-Reported Outcomes Measurement Information System (PROMIS)	Change from baseline in PROMIS Anxiety score	ANCOVA with LOCF	mITT	LEB 250 mg Q2W vs PBO; Week 16	Secondary analysis

Measure	Variable	Analysis Method (Section 6.1)	Population (Section 6.1.1)	Comparison/Time Point	Analysis Type
	Change from baseline in PROMIS Depression score				

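### Percent change in Sleep-loss and Skin Pain is analysed with no minimum baseline and no rule for a baseline of zero

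*SAP*

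**What the plan says.** - **Analysis.** SAP Table KGAK.6.7 (Section 6.10) lists "Percent Change from baseline in Sleep-loss Score" and "Percent Change from baseline in Skin Pain Score" with ANCOVA and MCMC-MI, labelled secondary, in the mITT population with no baseline restriction. The responder analyses on the same scales are restricted to baseline Sleep-loss of at least 2 and baseline Skin Pain of at least 4.
- **Method table.** SAP Table KGAK.6.4 (Section 6.4) assigns MCMC-MI with ANCOVA to "EASI percent change, Pruritus NRS percent change, Skin Pain NRS percent change, and Sleep-loss change from baseline". So it names percent change for Skin Pain and change for Sleep-loss.
- **Derivation.** SAP Table KGAK.6.6 defines "Percent change from baseline in Sleep-loss prorated weekly mean score", and its Skin Pain counterpart, as 100 × (observed − baseline) / baseline. The only rule for gaps is "Missing if baseline or observed value is missing".
- **Scales and entry.** Zero is a valid answer on both scales: Sleep-loss runs from 0 to 4 (Protocol 8.1.3.2), and Skin Pain is an "11-point horizontal scale anchored at 0 and 10" (Protocol 8.1.3.3). Protocol 5.1 sets minimums for EASI, IGA and BSA only.
- **Status of the endpoints.** Protocol Section 3 makes Sleep-loss change a secondary endpoint and Skin Pain exploratory. Percent change in Sleep-loss is not a protocol endpoint.

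**The concern.** A ratio to baseline needs a baseline clearly above zero. Nothing in the entry criteria secures that here, and the SAP allows for low values: Section 6.7.1 tabulates baseline Sleep-loss below 2 and Skin Pain below 4.

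Two things follow. A participant with an observed baseline of 0 has no percent change, and no rule says what happens next. The programmer would have to decide whether that participant drops out of an mITT analysis in which imputation is meant to keep everyone. Participants just above 0 can also contribute very large positive values to an ordinary least-squares model. SAP Section 6.1.2 specifies treatment, baseline and stratification terms, with no transformation or robust option. At stake is the precision of two labelled secondary analyses.

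**Working it through.** **1. Planned figures.** The SAP gives none for these analyses. Its only design figures are the Wald 90% half-widths in Section 5.2, which reproduce: 1.645 × √(2 × 0.83 × 0.17 / 109) = 0.084 and 1.645 × √(2 × 0.90 × 0.10 / 109) = 0.067. This point does not depend on them.

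**2. Baseline of 0.** The formula divides by 0. Multiple imputation does not help, because it is the denominator that is zero and it is observed. After rescue medication or discontinuation for lack of efficacy, Section 6.4.1 sets the value to baseline, so the result is (0 − 0)/0.

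**3. Small baselines.** The baseline weekly mean uses 4 to 7 daily whole-number scores (SAP 6.1.2), so the smallest non-zero value is 1/7 = 0.143.
- From 0.143 to 1.0: 100 × (1 − 0.143)/0.143 = +600%.
- From 0.143 to the scale maximum: +2700% for Sleep-loss, +6900% for a 0-to-10 scale.
- A 1-point rise is +200% from 0.5, and +14% from 7.

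**4. Effect on precision.** The inputs are assumed, since the documents give no baseline distribution, SD or effect for these scores. The simulation has 120 per arm and 1000 replicates, with true reductions of 25% on placebo and 50% on active and additive variation at follow-up. The ANCOVA has treatment and baseline only; the IGA stratum and the imputation are left out. Low baseline means below 1 for Sleep-loss and below 2 for the 0-to-10 scales. The floor in the table removes those participants.

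| Assumed baseline mean, SD | Zero baselines expected in 240 | Low-baseline share of participants → of residual sum of squares | SE of percent-change difference, all → with floor | Information kept |
|---|---|---|---|---|
| Sleep-loss 2.5, 0.8 | 0.1 | 3% → 23% | 4.8 → 4.1 | 57% |
| Sleep-loss 2, 1 | 2.6 | 14% → 67% | 8.6 → 5.0 | 24% |
| Sleep-loss 1.5, 1 | 6.7 | 27% → 81% | 12.3 → 6.0 | 15% |
| Skin Pain 6, 2.5 | 0.2 | 5% → 51% | 8.3 → 4.8 | 24% |
| Skin Pain 5, 3 | 1.0 | 15% → 81% | 16.3 → 5.5 | 7% |
| Pruritus 7, 2 | about 0 | 0.6% → 8.5% | 4.35 → 4.05 | 68% |
| Pruritus 7.5, 1.5 | 0 | about 0 → 0.2% | 3.60 → 3.60 | 88% |

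Information kept is (estimate/SE)² for percent change divided by (estimate/SE)² for absolute change. For Sleep-loss at mean 2: (22.42/8.61)² / (0.465/0.087)² = 6.78/28.57 = 0.24. For Skin Pain at mean 5: (21.45/16.30)² / (1.136/0.233)² = 1.73/23.77 = 0.07. The Pruritus rows use the same 0-to-10 model, so they also show what Skin Pain would give at such high baselines.

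**5. Effect on the estimate.** The floor moves the treatment difference little. The largest shift in the table is from −19.8 to −22.1 percentage points (Sleep-loss, mean 1.5).

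**6. Sensitivity to the assumptions.** Other assumed inputs, with 110 per arm, kept 21% to 52% for Sleep-loss and 12% to 32% for Skin Pain. The direction is stable; the size is not. Runs at the SAP's own cut-offs of 2 and 4 either helped precision or did no harm.

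**The case against.** The strongest case against has four parts.

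- **Much of the remedy is already planned.** Table KGAK.6.4 gives Sleep-loss change the ANCOVA with MCMC-MI, Table KGAK.6.7 also lists absolute change for Skin Pain, and the responder analyses carry floors. This stands, and it makes the correction small. It does not supply a rule for baseline 0 or say which variable leads.
- **The tables may agree.** A reader might infer that Table KGAK.6.7 puts percent change in place of absolute change for Sleep-loss and so contradicts Table KGAK.6.4. The text does not settle that. The table appears to have used merged cells that did not survive extraction, and both variables may share both methods. What can be asked for is explicit wording.
- **Dominance is unproven.** A reader might infer that the results would be dominated by participants with tiny baselines, or that a fixed share of information is lost. Neither follows from the documents. The low-baseline share of residual variation for Sleep-loss runs from 23% to 81% with the assumed baselines alone.
- **Pruritus is different.** A reader might extend the point to "Percentage change in Pruritus NRS from baseline". That percent change is a protocol secondary endpoint stated without restriction, and pruritus is an essential feature of the diagnostic criteria required for entry (Protocol Appendix 8). Under high assumed baselines almost no zeros arise and a floor hardly changes the SE. Restricting it would narrow a protocol endpoint for little gain.

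Loss of power also carries limited weight, because Protocol 9.1 calls the study descriptive with no planned hypothesis testing.

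**Conclusion.** The point holds for Sleep-loss and Skin Pain. That percent change has no minimum baseline, is undefined at an observed baseline of 0 and has no rule for that case follows from the documents alone. The cost in precision rests on assumed baselines. It runs from little at high baselines (12% of the information lost at mean 7.5, SD 1.5 on a 0-to-10 scale), through 43% in the most favourable Sleep-loss case, to well over half where baselines are low or widely spread. The shift in the estimate is small.

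The consequence is minor. The co-primary vaccine responses are unaffected, Skin Pain is exploratory in the protocol, and Sleep-loss percent change is an SAP addition. It is still worth correcting, because the better-behaved variable comes from the same data.

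**What to change.** 1. Make baseline-adjusted absolute change the lead ANCOVA with MCMC-MI analysis for Sleep-loss, as in the protocol and Table KGAK.6.4, and for Skin Pain.
2. If percent change is kept for these two scores, label it supplementary and restrict it to baseline Sleep-loss of at least 2 and Skin Pain of at least 4. These cut-offs are already in the SAP, so no new threshold is chosen after unblinding, and they remove every zero baseline.
3. Reword the Sleep-loss row of Table KGAK.6.7 so that it explicitly matches Table KGAK.6.4. Update the Skin Pain entries in Tables KGAK.4.1, KGAK.6.4 and KGAK.6.7 and in Section 6.4.1 to match.
4. Leave the Pruritus percent-change endpoint unrestricted.
5. Record the change and its reason as made after the Week 16 database lock, which SAP Version 3 already post-dates.

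The cost is SAP wording and small programming changes. Percent change would no longer be reported for participants with low baselines on these two scales. That group could be large: if the Sleep-loss baseline mean were 2 with a symmetric spread, about half would fall below the cut-off. Direct comparison with percent-change results from other studies would also be reduced.

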6.10.1. Primary Outcome and Methodology

The primary analysis of the study is to confirm that lebrikizumab 250 mg Q2W is the same as placebo when evaluating the booster response to the Tdap vaccine and the response to positive antibody response to MCV (Group C serum bactericidal antibodies) (proportion of participants) at Week 16 in the PPS population.

The primary estimand addresses the treatment response as directed. A 90% CI for the difference of proportion between treatment groups will be constructed using the stratified Newcombe approach (Yan and Su 2010; Kim and Won 2013) for each of the coprimary endpoints separately. Missing values will not be imputed. Descriptive statistics of antitetanus toxoid IgG antibody concentration (including the number of participants, mean, standard deviation, median, minimum, maximum, geometric mean, and coefficient of variation) and Meningococcal Group C serum rSBA titers (including the number and percentage of participants in each titer level) at Week 0, Week 12, and Week 16 will also be provided.

Primary outcomes booster response to the Tdap vaccine and the response to positive antibody response to MCV (Group C serum bactericidal antibodies), and the analysis are described in [Table KGAK.6.6](#).

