
 To compare the seroresponses to the Tdap and MCV between lebrikizumab-treated and placebo-treated participants with moderate-to-severe AD 	
The percentage of participants who:
 
 Develop a booster response to tetanus toxoid 4 weeks after the administration of the Tdap vaccine (Week 16) 
Booster response is defined as:
 
 ≥4-fold increase in anti-tetanus toxoid IgG antibody concentration if the pre-vaccination level was >0.10 IU/mL and ≤2.7 IU/mL; OR ≥2-fold increase in anti-tetanus toxoid IgG antibody concentration if the pre-vaccination level was >2.7 IU/mL; OR ≥4-fold increase in anti-tetanus toxoid IgG antibody concentration and a post-vaccination level ≥0.10 IU/mL if the pre-vaccination level was ≤0.10 IU/mL 
 Have positive antibody response to MCV (group C serum bactericidal antibodies) 4 weeks after the administration of the vaccine (Week 16) 
Positive antibody response to MCV is defined as:
 
 post-vaccination hSBA titer ≥4 times the LLOQ, if the pre-vaccination hSBA titer is less than the LLOQ; OR post-vaccination hSBA titer ≥4 times the pre-vaccination titer, if the pre-vaccination hSBA titer is greater than or equal to the LLOQ

Objectives	Endpoints
Secondary	

 To compare the efficacy of lebrikizumab with that of placebo in treatment of participants with moderate-to-severe AD, as measured by: 	
Percentage of participants at Week 16 achieving:
 
 an IGA score of 0 or 1 and a reduction of ≥ 2 points from baseline EASI-75 EASI-90 ≥ 4-point improvement from baseline in Pruritus NRS score 
Percentage change from baseline to Week 16 in:
 
 EASI Pruritus NRS score 
Change from baseline in:
 
 Percent BSA Sleep-Loss score

 To compare the patient-reported outcomes between lebrikizumab-treated and placebo-treated participants with moderate-to-severe AD, as measured by: 	
Change from baseline by visit in:
 
 PROMIS® Anxiety measure PROMIS® Depression measure
Exploratory	

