9.1. Statistical Hypotheses

Study KGAK is a descriptive study with no planned hypothesis testing. Confidence intervals (CIs) will be used to compare seroresponses for lebrikizumab- and placebo-treated participants.

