
 To compare the seroresponses to the Tdap and MCV between lebrikizumab-treated and placebo-treated participants with moderate to severe AD 	
The percentage of participants who:
 
 1. Develop a booster response to tetanus toxoid 4 weeks after the administration of the Tdap vaccine (Week 16) Booster response is defined as: 
 ○ ≥ 4-fold increase in antitetanus IgG antibody concentration if the prevaccination level was >0.10 IU/mL and ≤ 2.7 IU/mL; OR ○ ≥ 2-fold increase in antitetanus IgG antibody concentration if the prevaccination level was >2.7 IU/mL; OR ○ ≥ 4-fold increase in antitetanus IgG antibody concentration and a postvaccination level ≥ 0.10 IU/mL if the prevaccination level was ≤ 0.10 IU/mL 2. Have positive antibody response to Meningococcus C antigen of the MCV 4 weeks after the administration of the vaccine (Week 16) Positive antibody response to Meningococcus C antigen of the MCV is defined as: 
 ○ postvaccination rSBA titer ≥ 4 times the LLOQ, if the prevaccination rSBA titer is less than the LLOQ; OR ○ postvaccination rSBA titer ≥ 4 times the prevaccination titer, if the prevaccination rSBA titer is greater than or equal to the LLOQ

Objectives	Endpoints
Secondary	

 To compare the efficacy of lebrikizumab with that of placebo in the treatment of patients with moderate-to-severe AD To compare the patient-reported outcomes between lebrikizumab-treated and placebo-treated participants with moderate-to-severe AD 	
Percentage of participants at Week 16
 
 with an IGA score of 0 or 1 and a reduction of ≥ 2 points from baseline achieving EASI 75 achieving EASI 90 achieving ≥ 4-point improvement from baseline in Pruritus NRS score who had baseline Pruritus NRS ≥ 4 
Percentage change from baseline to Week 16 in
 
 EASI Pruritus NRS 
Change from baseline to Week 16 in
 
 BSA Sleep-loss score

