6.2.1. Primary Estimand for Primary Endpoints

The primary estimand that will be used to analyze primary endpoints will include data collected for participants who are in the per-protocol set (PPS). Missing values will not be imputed.

The primary estimand (principal stratum estimand) for primary endpoints is described by the following attributes:

- Population: PPS population as defined in [Table KGAK.6.1](#)
- Endpoint: Apply to 2 primary endpoints, seroresponses to the Tdap and MCV, as defined in [Table KGAK.4.1](#)

- How to account for ICEs: The ICEs are captured through the population definition
- Population-level summary: Difference in response proportions between treatment conditions

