Week 16 DBL: An unblinded interim analysis will be performed at the time (that is, a cut-off date) the last participant completes Week 16 or the ETV from the study. At the time of Week 16 DBL, the primary endpoint analysis related to booster response to tetanus toxoid has been performed. At the time of Week 16 DBL, the MCV hSBA data is considered as invalid because the assay procedure was not successfully validated at Eurofins Scientific®. Only a small group of statisticians working on the data analysis at the time of the Week 16 DBL had access to the patient-level data. A small internal group of Lilly personnel have been unblinded with a high-level summary result including Global Patient Safety and Medical study team representatives. The patient-level data was quarantined once MCV issues were identified. Personnel who have access to the patient-level data have no access to the biospecimen for the MCV hSBA. The primary endpoint analysis related to MCV response will be on hold until final DBL.

The study will not be terminated early on the basis of efficacy following these interim analyses.

Final DBL: A final DBL will occur after all participants have completed the safety follow-up period of the study, discontinued current study, or enrolled into the long-term extension study DRM06-AD07.

Lilly identified Nixelis as an alternate vendor for analyzing the MCV response using a fully validated rabbit complement serum bactericidal assay (rSBA) in order to deliver results for the final DBL and for analysis. The final DBL will include all data collected by the date of final DBL except Eurofins hSBA data. Final DBL will not occur until new fully validated rSBA is completed by Nixelis and all MCV response data is transferred. The primary endpoint analysis related to booster response to tetanus toxoid will be performed with the Eurofins Tdap data that

is a retransfer of the Week 16 DBL Eurofins Tdap data. The primary endpoint analysis related to MCV response will be performed with the Nexelis retested rSBA data based on the biospecimen collected through Week 16 DBL. For other efficacy and safety analysis, all data collected by the date of final DBL will be included.

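### SAP 6.10.1 sets out to confirm that lebrikizumab is the same as placebo on vaccine response, but the study is descriptive and no margin or interval rule defines sameness

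*SAP*

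**What the plan says.** SAP Section 6.10.1 opens with the aim of the primary analysis: "The primary analysis of the study is to confirm that lebrikizumab 250 mg Q2W is the same as placebo", for the tetanus booster response and the meningococcal C response at Week 16 in the per-protocol set. The method follows: "A 90% CI for the difference of proportion between treatment groups will be constructed using the stratified Newcombe approach", for each co-primary endpoint separately and without imputation.

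Other sections describe the task differently:

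- Protocol Section 9.1: "Study KGAK is a descriptive study with no planned hypothesis testing". It then gives the interval its role: "Confidence intervals (CIs) will be used to compare seroresponses for lebrikizumab- and placebo-treated participants".
- Protocol Section 3, objective: "To compare the seroresponses to the Tdap and MCV between lebrikizumab-treated and placebo-treated participants with moderate-to-severe AD". SAP Table KGAK.4.1 repeats this.
- SAP Section 6.2.1, primary estimand: "Population-level summary: Difference in response proportions between treatment conditions".

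Protocol Section 9.2 and SAP Section 5.2 justify the sample size by the expected width of a Wald 90% interval when the two observed rates are equal. They do not use power against a margin.

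**The concern.** Confirming sameness requires a statement, made in advance, of how large a difference would still count as the same, and a rule linking the interval to that limit. Neither document has one. A two-sided 90% interval is the one used for two one-sided 5% tests of equivalence, but without a margin it leads to no decision. The general two-sided 0.05 level in SAP Section 6.1 applies to tests of difference and does not fill the gap.

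The effect of lebrikizumab on vaccine response is the main purpose of the study. A report written to the SAP sentence could declare the arms the same, and with no rule to hand its author might simply check whether the interval contains 0. An interval can contain 0 because the arms are alike or because the estimate is imprecise. Here it would often contain 0 when lebrikizumab truly reduced the response.

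**Working it through.** **Inputs from the documents** (Protocol 9.2, SAP 5.2): 240 randomised 1:1, 218 evaluable, so 109 per arm. Planning rates, the same in both arms, are 83% for tetanus and 90% for MCV. The interval is two-sided 90%, so z = 1.645.

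**The plan's own figures.** The Wald half-width is z × √(2p(1−p)/n).

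- Tetanus: 1.645 × √(2 × 0.83 × 0.17 / 109) = 0.0837; the plan gives ±0.08.
- MCV: 1.645 × √(2 × 0.90 × 0.10 / 109) = 0.0668; the plan gives ±0.07.

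Both reproduce. The unstratified Newcombe interval gives 0.0842 and 0.0688, the same after rounding.

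**Could ±0.08 and ±0.07 be implied margins?** The documents do not call them margins. An interval with half-width 0.084 centred on 0 does not fit inside ±0.08. With identical true rates, the tetanus interval falls wholly within ±8 points in only about 2% of trials. What 109 per arm could confirm depends entirely on the missing margin. With assumed margins and equal true rates, the chance that the 90% interval lies wholly inside is:

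| Assumed margin | Tetanus (83%) | MCV (90%) |
|---|---|---|
| 5 points | 0% | 0% |
| 10 points | 26% | 55% |
| 15 points | 81% | 95% |

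**If containing 0 were read as sameness.** This reading and the loss sizes are assumptions. Let d = p₁ − p₂ (lebrikizumab minus placebo), with lᵢ and uᵢ the 90% Wilson limits for each arm. The Newcombe limits are

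- lower = d − √((p₁ − l₁)² + (u₂ − p₂)²)
- upper = d + √((u₁ − p₁)² + (p₂ − l₂)²)

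Probabilities come from summing over every pair of outcomes of two binomials with n = 109. Chance that the interval contains 0:

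| True loss | Tetanus (placebo 83%) | MCV (placebo 90%) |
|---|---|---|
| 5 points | 76% | 70% |
| 10 points | 44% | 33% |
| 15 points | 17% | 9% |

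**What the interval shows in those trials.** Take a true 10-point loss with 0 inside the interval.

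- The mean lower limit is -14 points (tetanus) and -13 points (MCV).
- The lower limit is below -10 in 88% and 84% of them.
- The chance that the interval both contains 0 and has a lower limit of -10 or higher is 0.442 × (1 − 0.884) = 0.051 for tetanus and 0.326 × (1 − 0.843) = 0.051 for MCV.

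**Worked example.** 83/109 against 90/109 is 0.7615 − 0.8257 = −0.0642. The Wilson limits are 0.6885 to 0.8218 and 0.7582 to 0.8774.

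- Lower: −0.0642 − √(0.0730² + 0.0517²) = −0.154
- Upper: −0.0642 + √(0.0603² + 0.0675²) = 0.026

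The interval, −15.4 to 2.6 points, contains 0 but does not exclude a 15-point loss.

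**Stratification.** The planned interval is stratified by baseline IGA. Simulating the stratified Newcombe interval with assumed per-arm splits of 65/44, 55/54 and 87/22, and common rates across strata, gives 0.440 (tetanus) and 0.326 (MCV) at a 10-point loss for every split. The unstratified figures are therefore adequate.

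**The case against.** The strongest reply is that nothing to be computed depends on the sentence. Both documents specify the same output: a 90% stratified Newcombe interval for each endpoint in the per-protocol set, with no success rule and no imputation. Protocol 9.1 still governs, and the published interval would itself reveal a possible loss. At a true 10-point loss the lower limit falls below -10 in about 95% of all trials. All of this is correct, and it is why the estimates are not in question. It does not rescue the sentence, which states what the primary analysis is meant to establish and leaves a reader free to cite either document.

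Four narrower points:

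- Comparing responses and estimating a difference in proportions are both compatible with a sameness aim. This stands. The direct conflict is with Protocol 9.1; the objective and the estimand only fail to supply a criterion.
- The percentages describe a possible misreading and are not an error rate of the plan. This stands, and they should be read as illustration.
- The 90% MCV rate is attributed to the human-complement assay in Protocol 9.2 and to the rabbit-complement assay in SAP 5.2, from the same cited study, so its application to the assay now planned is uncertain. This stands as a caveat. With assumed placebo rates of 85% and 95%, the same enumeration gives 41% and 19% at a 10-point loss, against 33% at 90%.
- Reconciling the documents needs only the estimation wording, and a statement about the lower limit goes further and is one-sided. That is partly fair. But the statement is a correct reading of the planned interval, sets no threshold, and points to the direction that matters for a possible loss of response. The full interval is still reported.

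**Conclusion.** The concern holds. SAP 6.10.1 assigns the primary analysis a confirmatory aim that Protocol 9.1 rules out and that no margin or interval rule supports. The design can estimate the difference in each seroresponse rate; it cannot confirm that the arms are the same.

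The size depends on how the gap is filled. If containing 0 is taken as sameness, a true 10-point loss passes in 44% of trials for tetanus and 33% for MCV, and a 5-point loss in 76% and 70%. These figures assume that reading, illustrative loss sizes, 109 evaluable per arm and the documents' planning rates. The sample-size intervals in Protocol 9.2 and SAP 5.2 are arithmetically correct for equal observed rates. This should be corrected because it affects the study's main conclusion, although the planned estimates are unaffected.

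**What to change.** Replace the opening sentence of SAP Section 6.10.1 with:

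> The primary analysis is to estimate the difference (lebrikizumab minus placebo) in each seroresponse rate in the PPS with a 90% CI. A CI containing 0 will not be taken as evidence of sameness; the lower 90% limit will be reported as the largest loss of response not excluded.

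Carry the same wording into the clinical study report.

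Do not add a margin for tetanus. SAP Section 6.16 records that at the Week 16 lock "the primary endpoint analysis related to booster response to tetanus toxoid has been performed", and SAP Version 3 was approved after that lock, so a tetanus margin set now would be post hoc. The proposed wording needs none for MCV either. Leave Protocol 9.2 and SAP 5.2 unchanged on this point.

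The cost is one SAP sentence. Data, endpoints, population and interval method stay as they are. The downside is a weaker headline claim.
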